PI	Principal Investigator
PK	Pharmacokinetics
QD	Once Daily ("quaque die")
SAE	Serious Adverse Event
SAP	Statistical Analysis Plan
SD	Standard Deviation
SUSAR	Suspected Unexpected Serious Adverse Reaction
TCPS	Tri-Council Policy Statement
TEAE	Treatment Emergent Adverse Event
T _{max}	Time to Reach Maximum Concentration
US	United States
WI-NRS	Worst Itch – Numeric Rating Score

1. PROTOCOL SUMMARY

1.1 Synopsis

Protocol Title:	A Phase 1/2b, Multiple Dose and 12-Week, Parallel Group, Double Blind, Dose Ranging, Vehicle-Controlled Study of the Safety and Efficacy of ARQ-252 Cream 0.1% and ARQ-252 Cream 0.3% in Subjects with Chronic Hand Eczema
Clinical Indication:	Chronic Hand Eczema (CHE)
Investigational Product:	ARQ-252 cream will be supplied as ARQ-252 cream 0.1% (only applicable in Cohort 2) and ARQ-252 cream 0.3%. Matching vehicle cream (only applicable in Cohort 2) will contain only excipients of ARQ-252 cream. The active ingredient in ARQ-252 cream is SHR0302, a selective JAK1 inhibitor.
Study Design:	ARQ-252-205 is a Phase 1/2b, Multiple Dose and 12-week, parallel group, double blind, vehicle-controlled study of the safety and efficacy of ARQ-252 cream 0.1% and ARQ-252 cream 0.3% in subjects with chronic hand eczema. There are 2 cohorts of subjects. 
 • Cohort 1 is a multiple dose cohort in which subjects with chronic hand eczema will be assigned to ARQ-252 cream 0.3% QD x 2 weeks to be applied to both hands (approximately 4% of BSA). PK and tolerability will be evaluated. • Cohort 2 is a parallel group, double blind, vehicle-controlled cohort in which subjects with chronic hand eczema will be randomized to ARQ-252 cream 0.3% QD, ARQ-252 cream 0.3% BID, ARQ-252 cream 0.1% QD, vehicle cream BID or vehicle cream QD x 12 weeks to be applied to both hands (approximately 4% of BSA). Safety and efficacy will be evaluated.
Study Objectives:	The objectives of this study are as follows: Phase 1 (Cohort 1) 
 • To assess the safety, tolerability and PK of QD application of ARQ-252 0.3% to both hands for 2 weeks in 6 subjects with chronic hand eczema (Cohort 1) Phase 2b (Cohort 2) 
 • To assess the safety and efficacy of ARQ-252 cream 0.1% QD and ARQ-252 cream 0.3% QD and BID, vs vehicle applied QD and BID for 12 weeks to subjects with chronic hand eczema (Cohort 2)
Study Sites:	Approximately 45 sites in the United States, Canada and Australia.


Study Population:
	
For both Cohorts, subjects will be male and female adults (≥ 18 years of age), with chronic hand eczema, and an Investigator's Global Assessment (IGA) of disease severity of at least Mild ('2') at Baseline. In Cohort 2, subjects with IGA of 'Mild' will be limited to 20% of total enrollment, and subjects with IGA of 'Severe' will also be limited to 20% of total enrollment.
 
 • Cohort 1 will include approximately 6 evaluable subjects, assigned to ARQ-252 cream 0.3% QD • Cohort 2 will include approximately 215 subjects, randomized 2:2:1:1:1 to ARQ-252 cream 0.3% QD : ARQ-252 cream 0.3% BID : ARQ-252 cream 0.1% QD : vehicle cream BID: vehicle cream QD

Duration of Participation for Subjects:
	
Cohort 1: Screening (up to 4 weeks), Treatment phase (2 weeks), and follow-up (1 week post-treatment completion) for a total of 7 weeks
 
Cohort 2: Screening (up to 4 weeks), Treatment phase (12 weeks), and follow-up (1 week post-treatment completion); for a total of 17 weeks


Inclusion Criteria:
	
 1. Participants legally competent to sign and give informed consent. 2. Males and females 18 years of age and older (inclusive) at the time of consent. 3. Clinical diagnosis of chronic hand eczema, defined as hand eczema persistent for more than 3 months, or returned twice or more within the last 12 months (Diepgen 2009). Generally stable disease for 6 weeks. Both irritant and non-irritant etiologic forms are allowed. All morphologic types are allowed, e.g., vesicular/dyshidrotic, hyperkeratotic, nummular, and other types. 4. An Investigator's Global Assessment of disease severity (IGA) of at least Mild ('2') at Baseline (Visit 2). (In Cohort 2, subjects with IGA of 'Mild' will be limited to 20% of total enrollment, and subjects with IGA of 'Severe' subjects will also be limited to 20% of total enrollment). 5. Chronic hand eczema involving at least 0.3% body surface area total (i.e., approximately a third of one handprint) lesions on both hands added together at Baseline (Visit 2). 6. Female subjects of childbearing potential (FOCBP) must have a negative serum pregnancy test at Screening and negative urine pregnancy test at Baseline (Visit 2). For FOCBP involved in any sexual intercourse that could lead to pregnancy: the subject must agree to use a highly effective contraceptive method for at least 4 weeks prior to Day 1. Additionally, from Day 1 until at least 4 weeks after the last investigational product administration, these

	
subjects must agree to use at least 1 highly effective contraceptive method in addition to 1 barrier method according to Contraception Requirements (Figure 1).
 
 7. Females of non-childbearing potential must either be post-menopausal with spontaneous amenorrhea for at least 12 months (post-menopausal status will be confirmed with FSH testing) or have undergone surgical sterilization (permanent sterilization methods include hysterectomy, bilateral oophorectomy, hysteroscopic sterilization or bilateral salpingectomy) according to Contraception Requirements (Figure 1). 8. Males, if engaging in sexual intercourse with a female who is pregnant or a female of childbearing potential, must agree to use a condom every time during the study and every time subsequently until 4 weeks after the last investigational product administration. 9. Males must agree not to donate sperm from the first dose of investigational product until 4 weeks after the last investigational product administration. 10. Subjects in good health as judged by the Investigator, based on medical history, physical examination, 12-lead electrocardiogram (ECG), serum chemistry labs, hematology values, and urinalysis. 11. Subjects are considered reliable and capable of adhering to the Protocol and visit schedule, according to the judgment of the Investigator.

Exclusion Criteria:
	
 1. Concurrent skin diseases on the hands which, in the opinion of the Investigator, could confound the study (e.g., tinea manuum). 2. Active skin diseases not on the hands such as atopic dermatitis or psoriasis requiring medical treatment that could significantly affect hand eczema, in the Investigator’s opinion. 3. Subjects with any presence or history of psoriasis. 4. History of a positive patch test with continued exposure to allergen. If, in the opinion of the Investigator, there is any suspected allergic hand eczema with continued exposure to allergen, subject must undergo diagnostic patch testing to determine if they meet entry criteria prior to Baseline (Visit 2). 5. Subjects who cannot discontinue systemic and/or topical therapies for the treatment of chronic hand eczema prior to Baseline (Visit 2) and during the study according to Excluded Medications and Treatments (Table 2), (i.e., immunosuppressive drugs, immunomodulating drugs, retinoids, or corticosteroids). 6. Psoralen ultraviolet A (PUVA) or ultraviolet B (UVB) therapy on the hands within 4 weeks prior to Baseline (Visit 2).

	
7. Cutaneously applied treatment with immunomodulators (e.g., phosphodiesterase-4 (PDE-4) inhibitors, pimecrolimus, tacrolimus), topical urea moisturizers, topical antibiotics, or low or mid potency topical corticosteroids on the hands or elsewhere within 1 week prior to Baseline (Visit 2). Cutaneously applied treatment with high potency topical corticosteroids on the hands or elsewhere within 2 weeks prior to Baseline (Visit 2).8. Subjects that have significant active systemic or localized infection, including known actively infected eczema or have had any infection that required oral or intravenous administration of antibiotics, antifungal or antiviral agents within 2 weeks prior to Baseline (Visit 2).9. Other cutaneously applied therapy on the hands (except for the use of subject's own non-urea and non-salicylic acid emollients) within 1 week prior to Baseline (Visit 2).10. Subjects who are unwilling to refrain from using a tanning bed or other LEDs as well as outdoor tanning or excessive sun exposure for 4 weeks prior to Baseline (Visit 2) and during the study.11. Subjects with a history of chronic alcohol or drug abuse within 6 months prior to Baseline (Visit 2).12. Current or a history of cancer within 5 years with the exception of fully treated skin basal cell carcinoma, cutaneous squamous cell carcinoma or carcinoma in situ of the cervix.13. Subjects that have received live vaccine therapy less than 4 weeks prior to Baseline (Visit 2), immunosuppressive drugs less than 4 weeks prior to Baseline (Visit 2), or have known infection with mycobacterium tuberculosis, hepatitis B or C, or HIV, or have a diagnosis of an immunodeficiency disorder.14. Subject had a major surgery within 4 weeks prior to Baseline (Visit 2) or has a major surgery planned during the study.15. Known or suspected:
• severe renal insufficiency or severe hepatic disorders• hypersensitivity to component(s) of the investigational product which include SHR0302, butylated hydroxytoluene (BHT), benzyl alcohol, dimethyl sulfoxide, cyclomethicone, dimethicone (350 cst), ST-Elastomer 10, water, propylene glycol, polyethylene glycol 200, Pemulen TR1, Carbopol 974P, ethylenediaminetetraacetic acid, trolamine and D-limonene.16. Pregnant or lactating women or women planning to become pregnant during the study and / or within 28 days following the last dose of investigational product.
--	--

[figure not shown]
	
17. Subjects who cannot discontinue the use of strong systemic Cytochrome P-450 3A4 inducers e.g., efavirenz, nevirapine, glucocorticoids, barbiturates (including phenobarbital), phenytoin, rifampin and carbamazepine for 2 weeks prior to Baseline (Visit 2) and during the study period.
 
18. Subjects who cannot discontinue the use of strong systemic Cytochrome P-450 3A4 inhibitors e.g., indinavir, nelfinavir, ritonavir, clarithromycin, itraconazole, ketoconazole, fluconazole, nefazodone, saquinavir, suboxone and telithromycin for 2 weeks prior to Baseline (Visit 2) and during the study period.
 
19. Subjects with any serious medical condition or clinically significant laboratory, ECG, vital signs or physical examination abnormality that would prevent study participation or place the subject at significant risk, as judged by the Investigator.

Key Assessments:
	
Phase 1 (Cohort 1):
 
 • Safety will be monitored through application site assessments, safety labs, AEs, ECGs, physical examinations, and vital signs. • Serial PK sampling will be performed on Day 1 (1, 2, 4, 6, and 24 hours post-dose administration), and at Day 15 (pre-dose and 1, 2, 4, 6, and 24 hours post-dose administration). For 24-hour timepoints, subjects return to the clinic on the following day within 2 hours of the IP application time from the previous day for PK plasma sample collection. A pre-dose/trough PK sample will be taken at Day 8. 
Phase 2b (Cohort 2):
 
 • Safety will be monitored through application site assessments, safety labs, AEs, ECGs, physical examinations, and vital signs. • Efficacy will be evaluated through IGA, HECSI, WI-NRS Pruritus, NRS Pain, Nail Dystrophy Assessments and QOLHEQ • PK will be evaluated through trough/pre-dose sampling at Baseline, Day 29, and Day 85.

Study Endpoints:
	
Phase 1 (Cohort 1):
 
 • Safety, as measured by the incidence and severity of adverse events, changes in laboratory parameters, tolerability, and pharmacokinetics. 
Phase 2b (Cohort 2):
 
The primary endpoint of Cohort 2 is:
 
 • The rate of an IGA score of ‘clear’ or ‘almost clear’ at Week 12

	
Phase 2b (Cohort 2):
 
The secondary endpoints of Cohort 2 are:
 
• The rate of achievement of IGA of ‘clear’ or ‘almost clear’ PLUS at least a 2-point improvement from Baseline at Weeks 2, 4, 8 and 12• The rate of achievement of at least a 2-point improvement from Baseline at Weeks 2, 4, 8 and 12• Achievement of IGA of ‘clear’ or ‘almost clear’ at Weeks 2, 4, and 8• Time to IGA of ‘clear’ or ‘almost clear’• Change in IGA score at Weeks 2, 4, 8, and 12 as compared to Baseline• Change in WI-NRS pruritus score at 2 weeks, 4 weeks, 8 weeks, and 12 weeks compared to Baseline• The rate of achievement of ≥ 4-point reduction from Baseline in WI-NRS pruritus score at 2 weeks, 4 weeks, 8 weeks, and 12 weeks in subjects with Baseline WI-NRS pruritus score of at least 4• Time to the first achievement of ≥ 4-point reduction from Baseline in WI-NRS pruritus score in subjects with Baseline WI-NRS pruritus score of at least 4• Percent change in HECSI (Hand Eczema Severity Index) score at Weeks 2, 4, 8, and 12 compared to Baseline• Change in NRS Pain score at 2 weeks, 4 weeks, 8 weeks, and 12 weeks compared to Baseline• The rate of achievement of ≥ 4-point reduction from Baseline in Pain NRS score at 2 weeks, 4 weeks, 8 weeks, and 12 weeks in subjects with Baseline Pain NRS score of at least 4• Time to the first achievement of ≥ 4-point reduction from Baseline in Pain NRS score in subjects with Baseline Pain NRS score of at least 4• Change from Baseline in overall Quality of Life in Hand Eczema Questionnaire (QOLHEQ) score at each visit• Percent BSA affected by disease and % change from baseline in BSA affected by disease at baseline, 2 weeks, 4 weeks, 8 weeks, and 12 weeks. 
The exploratory endpoint of Cohort 2 is:
 
• Change from Baseline in Nail Dystrophy at each visit
--	--

Power and Sample Size:	
Cohort 1 will include approximately 6 evaluable subjects, which is deemed adequate for the purpose of evaluating safety and PK prior to Cohort 2.
 
There are approximately 215 subjects planned for Cohort 2. Approximately 61 subjects will receive ARQ-252 cream 0.3% QD, approximately 61 subjects will receive ARQ-252 cream 0.3% BID, approximately 31 subjects will receive ARQ-252 cream 0.1% QD, approximately 31 subjects will receive matching vehicle cream QD, and approximately 31 subjects will receive vehicle cream BID. The randomization scheme will be 2:2:1:1:1 between these 5 treatment groups, stratified by study site and IGA at Baseline.
 
The primary statistical comparisons will be to assess the ARQ-252 cream 0.3% BID group versus the vehicle BID group, to assess the ARQ-252 cream 0.3% QD group versus the vehicle QD group, and to assess the ARQ-252 cream 0.1% QD group versus the vehicle QD group.
 
A sample size of 55 per active arm and 28 per vehicle arm will provide approximately 85% power at the 2-sided 5% significance level to detect a difference in the percent of subjects with IGA clear or almost clear at Week 12; for each ARQ-252-treated group versus vehicle group within the same daily dosing frequency, assuming an active treatment response rate of 45% and a vehicle response rate of 15%, with a two-sided $\alpha = 0.1$. This is based on a 2-group X^2 test of equal proportions (without continuity correction). With a 10% dropout rate, the sample size for the study is increased to 61 subjects per active arm and 31 subjects per vehicle arm (215 subjects total).
 
The primary statistical comparisons and evaluation of the secondary endpoints will not be adjusted for multiplicity.

Statistical Analysis:	
Descriptive statistics will be presented for the study endpoints. This includes the number and percentage of subjects for binary endpoints/categorical data, and mean, SD, median, minimum, and maximum for continuous data.
 
The primary endpoint in Cohort 2 of 'IGA clear or almost clear at Week 12' will be analyzed using a Cochran-Mantel-Haenszel test stratified by study site and IGA at Baseline. The analysis will be performed on the Intention-to-Treat (ITT) population and missing data will be imputed using multiple imputation.
 
Continuous secondary endpoints measured in Cohort 2 will be analyzed using Analysis of Covariance with treatment and stratification factors as independent variables. The ITT population will be used. Binary secondary endpoints will be analyzed similarly to the primary endpoint.

	
All subjects who are randomized and receive at least one confirmed dose of investigational product will be included in the safety population.
 
Adverse events (AEs) will be summarized within each cohort by preferred term, system organ class, and treatment group (Cohort 2 only) for all treatment-emergent AEs, serious AEs, related AEs, AEs leading to withdrawal from investigational product.
 
Safety laboratory parameters and vital signs will be summarized at each visit using descriptive statistics or frequencies and percentages, as appropriate. Changes from Baseline in laboratory values and vital signs will also be summarized by visit. In addition, changes from Baseline in weight and laboratory values will be summarized using shift tables. These summaries will be tabulated by treatment group for Cohort 2.
 
All subjects who are enrolled and receive at least one application of investigational product and have sufficient pharmacokinetic assessments will be included in the pharmacokinetic population (Cohorts 1 and 2). When possible, the exposure to SHR0302 will be calculated based on plasma concentrations versus time profile data.

--	---

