1.2 Study Schema

[figure not shown]

A Phase 1/2b, Multiple Dose and 12-Week, Parallel Group, Double Blind, Dose Ranging, Vehicle-Controlled Study of the Safety and Efficacy of ARQ-252 Cream 0.1% and ARQ-252 Cream 0.3% in Subjects with Chronic Hand Eczema

Phase 1/Cohort 1

Approximately 6 subjects with chronic hand eczema will receive ARQ-252 0.3% cream QD (once daily)

Phase 2b (Cohort 2)

A Phase 1/2b, Multiple Dose and 12-Week, Parallel Group, Double Blind, Dose Ranging, Vehicle-Controlled Study of the Safety and Efficacy of ARQ-252 Cream 0.1% and ARQ-252 Cream 0.3% in Subjects with Chronic Hand Eczema

Phase 2b/Cohort 2

Approximately 215 subjects with chronic hand eczema will be randomized to receive either:

- ARQ-252 0.3% cream QD (once daily) N=61
- ARQ-252 0.3% cream BID (twice daily) N=61
- ARQ-252 0.1% cream QD (once daily) N=31
- Vehicle cream QD (once daily) N=31
- Vehicle cream BID (twice daily) N=31

The randomization scheme will be 2:2:1:1:1 between these 5 treatment groups, stratified by study site, and IGA at Baseline.

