6.1 Statistical Methods

The methodology presented below is a summary of the more detailed analysis plan that will be presented in the Statistical Analysis Plan (SAP). The SAP will be finalized before the database is locked and unblinded. Any changes to the methods described in the final SAP will be described and justified in the clinical study report.

All statistical processing will be performed using SAS[®] (Version 9.4) unless otherwise stated.

Descriptive statistics will be used to provide an overview of the safety, efficacy, and pharmacokinetic results. For categorical parameters, the number and percentage of subjects in each category will be presented. The denominator for percentage will be based on the number of subjects appropriate for the purpose of analysis. For continuous parameters, descriptive statistics will include n (number of subjects), mean, standard deviation (SD), median, minimum, and maximum.

Missing efficacy data for IGA will be imputed using multiple imputation.

The primary statistical comparisons and secondary endpoints will be made at the 0.10 significance level and will not be adjusted for multiple comparisons.

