6.1.1 Determination of Sample Size

Cohort 1 will include approximately 6 evaluable subjects, which is deemed adequate for the purpose of evaluating safety and PK prior to Cohort 2.

There are approximately 215 subjects planned for Cohort 2. Approximately 61 subjects will receive ARQ-252 cream 0.3% QD, approximately 61 subjects will receive ARQ-252 cream 0.3% BID, approximately 31 subjects will receive ARQ-252 cream 0.1% QD, approximately 31 subjects will receive matching vehicle cream QD, and approximately 31 subjects will receive vehicle cream BID. The randomization scheme will be 2:2:1:1:1 between these 5 treatment groups, stratified by study site and IGA at Baseline.

The primary statistical comparisons will be to assess the ARQ-252 cream 0.3% group BID group versus the vehicle BID group, to assess the ARQ-252 cream 0.3% QC group versus the vehicle QD group, and to assess the ARQ-252 cream 0.1% QD group versus the vehicle QD group. A sample size of 55 per active arm and 28 per vehicle arm will provide approximately 85% power at the 2-sided 10% significance level to detect a difference in the rate of subjects attaining an IGA score of clear or almost clear (for each ARQ-252-treated group versus vehicle group within the same daily dosing frequency), assuming an active treatment response rate of 45% and a vehicle response rate of 15%. This is based on a 2-group X² test of equal proportions (without continuity correction). With a 10% dropout rate, the sample size for the study would be increased to 61 subjects per active arm and 31 subjects per vehicle arm (215 subjects total).

The primary statistical comparisons and evaluations of secondary endpoints will not be adjusted for multiplicity.

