6.2 Efficacy Evaluation

6.2.1 Primary Efficacy Endpoint

The primary efficacy endpoint is the rate of subjects achieving an IGA score of ‘clear’ or ‘almost clear’ at Week 12.

The primary statistical comparisons will be to assess the ARQ-252 cream 0.3% group BID group versus the vehicle BID group, to assess the ARQ-252 cream 0.3% QD group versus the vehicle QD group, and to assess the ARQ-252 cream 0.1% QD group versus the vehicle QD group.

The primary endpoint will be analyzed using a Cochran-Mantel-Haenszel test stratified by IGA at Baseline and study site. Statistical significance will be concluded at the 2-sided 10% significance level for each of the primary comparisons. Missing scores will be imputed using multiple imputation.

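### The synopsis attaches one 85% power figure to two alphas, and claims it at 55 per active arm for every ARQ-252 group although the 0.1% QD arm has only 31 randomized

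*Protocol*

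**What the plan says.** The Power and Sample Size entry of Protocol 1.1 states "A sample size of 55 per active arm and 28 per vehicle arm will provide approximately 85% power at the 2-sided 5% significance level". It assumes response rates of 45% on active and 15% on vehicle, and finishes the same sentence with a two-sided alpha of 0.1. The claim is made "for each ARQ-252-treated group versus vehicle group within the same daily dosing frequency", for a two-group chi-square test without continuity correction. A 10% dropout allowance then raises the sizes to 61 per active arm and 31 per vehicle arm, 215 in all.

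The same entry lists 61, 61, 31, 31 and 31 subjects for 0.3% QD, 0.3% BID, 0.1% QD and the two vehicle arms, randomized 2:2:1:1:1. It names 0.1% QD v vehicle QD as one of three primary comparisons. Protocol 1.2 confirms the arm size: "ARQ-252 0.1% cream QD (once daily) N=31". SAP 3.4 gives the same number.

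Elsewhere only 10% appears. Protocol 6.1: "The primary statistical comparisons and secondary endpoints will be made at the 0.10 significance level". Protocol 6.1.1: "approximately 85% power at the 2-sided 10% significance level". Protocol 6.2.1: "Statistical significance will be concluded at the 2-sided 10% significance level for each of the primary comparisons". SAP 3.2, 4.1 and 8.1.1 agree.

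The arm-size wording is not confined to the synopsis. Protocol 6.1.1 also starts from 55 per active arm and goes to "61 subjects per active arm and 31 subjects per vehicle arm (215 subjects total"). SAP 3.2 repeats 55 per active arm, and adds a power above 90% for each active arm, at 55, against 56 pooled vehicle subjects.

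**The concern.** One power figure cannot belong to both alphas at the same sample size, so the sentence is wrong for at least one of them. No power formula is named, so the reader cannot settle the matter from that sentence.

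The arm size matters more. A figure for 55 v 28 is claimed for every ARQ-252 group, and one of the three primary comparisons is really about 28 v 28. In a dose-ranging trial, a non-significant result for 0.1% QD should be read against that arm's own power. The documents give only the figure for an arm twice its size.

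**Working it through.** **Inputs.** Response rates 45% and 15%; 55 per active and 28 per vehicle arm; chi-square without continuity correction (Protocol 1.1 and 6.1.1). Arm sizes 61, 61, 31, 31, 31 (Protocol 1.1 and 1.2, SAP 3.4). Dropout 10%.

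**Step 1: try to reproduce 85% at 55 v 28.** The pooled-variance formula is

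power = Φ[(d − z·s0) / s1],

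with d = 0.30, s0 = √[p̄(1 − p̄)(1/n1 + 1/n2)] and s1 = √[p1(1 − p1)/n1 + p2(1 − p2)/n2].

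- p̄ = (55 × 0.45 + 28 × 0.15)/83 = 0.3488; s0 = 0.1106; s1 = 0.0952.
- Alpha 0.05 (z = 1.960): Φ(0.874) = 80.9%.
- Alpha 0.10 (z = 1.645): Φ(1.240) = 89.3%.

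Exact enumeration of the two binomials gives 82.2% and 90.0%. The noncentral chi-square approximation (1 df, noncentrality d²/s0² = 0.09/0.1106², about 7.35) gives 77.4% and 85.7%.

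So 85% is recovered at 10% by the noncentral approximation. It can also be recovered at 5% by pooled variance if the dropout-inflated sizes 61 v 31 are used (85.1%), but those are not the sizes the sentence gives. The two routes are incompatible, and the text does not say which was meant.

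**Step 2: 0.1% QD at its own size.** 31 × 0.9 = 27.9, so about 28 v 28. Then p̄ = 0.30, s0 = 0.1225 and s1 = 0.1157. At alpha 0.10, Φ(0.852) = 80.3%. At alpha 0.05, Φ(0.518) = 69.8%.

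The primary analysis keeps all randomized subjects: "The analysis will be performed on the Intention-to-Treat (ITT) population and missing data will be imputed using multiple imputation". If imputed subjects counted as full observations, the size would be 31 v 31; that is the upper bound.

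**Step 3: all comparisons at two-sided 10%.**

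| Comparison | n | Pooled variance | Exact | Noncentral |
|---|---|---|---|---|
| 0.3% arm v same-frequency vehicle | 55 v 28 | 89.3% | 90.0% | 85.7% |
| 0.1% QD v vehicle QD | 28 v 28 | 80.3% | 81.9% | 79.0% |
| 0.1% QD v vehicle QD, upper bound | 31 v 31 | 83.8% | 84.7% | 82.5% |
| 0.3% arm v pooled vehicle | 55 v 56 | 97.2% | 97.4% | 96.5% |
| 0.1% QD v pooled vehicle | 28 v 56 | 90.0% | 90.7% | 91.1% |
| 0.1% QD v pooled vehicle, upper bound | 31 v 62 | 92.4% | 92.9% | 93.4% |

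Against same-frequency vehicle, 0.1% QD (28 v 28) lies below the 0.3% arms (55 v 28) by 9.0, 8.1 and 6.7 points in the three columns.

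**Step 4: head counts.** Taken literally, the per-arm sizes give 3 × 55 + 2 × 28 = 221 before the dropout allowance, more than the 215 randomized, and 3 × 61 + 2 × 31 = 245 after it. The stated total is right only as 2 × 61 + 3 × 31 = 215, with 2 × 55 + 3 × 28 = 194 remaining after dropout. The total and the randomization are sound; the per-active-arm label is not.

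**The case against.** The best defence has four parts.

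- **The 5% is an obvious slip.** Its own sentence ends with 0.1, and every other statement uses 10%. That is so, and it fixes which figure to delete. It does not help someone who reads only the synopsis.
- **The 85% is not an arithmetic error.** One recognised approximation gives 85.7% at the operative alpha, and the other two make the figure conservative. This stands for the 0.3% arms; what is missing there is the name of the formula. It does not rescue 0.1% QD, for which that same approximation gives 79.0%, or 82.5% at the upper bound.
- **The true arm sizes are in the same synopsis entry.** They are, so nobody would enrol the wrong number. The power claim still uses a size that the third active arm does not have, and Protocol 6.1.1 and SAP 3.2 carry it forward.
- **The SAP tests against pooled vehicle.** SAP 4.1, 8.1.1 and 10 say so, and on that comparison 0.1% QD has about 90 to 91%, so the claim of more than 90% is essentially met. This is the strongest point and it limits the consequence. But SAP 3.2 still lists the same-frequency comparisons as primary with the 85%, and the protocol specifies only those.

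**Conclusion.** Both defects are in the text. The 5% in the synopsis is wrong, and 55 (or 61) per active arm does not describe 0.1% QD. For the 0.3% arms the stated 85% is at worst conservative at the operative 10% level. For 0.1% QD v vehicle QD it is too high by about 0 to 5 points by pooled variance or exact calculation, and by about 3 to 6 points by the noncentral approximation. The lower end of each range assumes that all 31 per arm contribute fully; the upper end assumes 28 per arm.

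All figures assume 45% v 15% and an unstratified chi-square. The planned analysis is a stratified CMH test with multiple imputation, and no adjustment for that has been made. Enrolment, the test and the decision rule are unaffected. The documents should still be corrected, because a named primary comparison has no power figure at its planned size.

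**What to change.** - Protocol 1.1: delete the 5% level and keep two-sided 10%.
- Protocol 1.1 and 6.1.1, and SAP 3.2: replace 55 per active arm with 55 per 0.3% arm and 28 in the 0.1% QD arm. In the two protocol places, replace 61 per active arm with 61 per 0.3% arm and 31 in the 0.1% QD arm.
- SAP 3.2: word the pooled-vehicle claim for each 0.3% arm of 55 and for the 0.1% QD arm of 28.
- Replace the single 85% with power by arm at two-sided 10%, and name the formula. By pooled variance: about 89% for each 0.3% arm and about 80% for 0.1% QD v same-frequency vehicle; about 97% and about 90% v pooled vehicle.
- State that these figures are for an unstratified chi-square, while the planned analysis is a CMH test stratified by pooled site group and baseline IGA.

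The cost is wording only: no extra patients and no change to the analysis. The stated power for 0.1% QD v vehicle QD falls from 85% to about 80%, and that for the 0.3% arms rises to about 89%.
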